6.5 Overdose

All occurrences of overdose must be reported as SAEs (see [Section 6.1.1](#) for reporting details).

6.6 Potential Drug Induced Liver Injury (DILI)

Wherever possible, timely confirmation of initial liver-related laboratory abnormalities should occur prior to the reporting of a potential DILI event. All occurrences of potential DILIs, meeting the defined criteria, must be reported as SAEs (see [Section 6.1.1](#) for reporting details).

Potential drug induced liver injury is defined as:

1. AT (ALT or AST) elevation > 3 times upper limit of normal (ULN)
AND
2. Total bilirubin > 2 times ULN, without initial findings of cholestasis (elevated serum alkaline phosphatase),
AND
3. No other immediately apparent possible causes of AT elevation and hyperbilirubinemia, including, but not limited to, viral hepatitis, pre-existing chronic or acute liver disease, or the administration of other drug(s) known to be hepatotoxic.

6.7 Other Safety Considerations

Any significant worsening noted during interim or final physical examinations, electrocardiogram, x-ray filming, any other potential safety assessment required or not required by protocol should also be recorded as a nonserious or serious AE, as appropriate, and reported accordingly.

7 DATA MONITORING COMMITTEE AND OTHER EXTERNAL COMMITTEES

A Data Monitoring Committee (DMC) will be established to provide oversight of safety and efficacy considerations in protocol CA209577. Additionally, the DMC will provide advice to the sponsor regarding actions the committee deems necessary for the continuing protection of subjects enrolled in the study. The DMC will be charged with assessing such actions in light of an acceptable benefit/risk profile for nivolumab. The DMC will act in an advisory capacity to BMS and will monitor subject safety and evaluate the available efficacy data for the study. The oncology therapeutic area of BMS has primary responsibility for design and conduct of the study.

When required, adjudicated events will be submitted to the DMC and Health Authorities for review on a specified timeframe in accordance with the adjudication documentation.

8 STATISTICAL CONSIDERATIONS

[figure not shown]
8.1 Sample Size Determination

The sample size determination takes into consideration the comparison of the primary endpoint of DFS and the first secondary endpoint of OS between the 2 treatment arms.

8.1.1 *Assumptions of the Control Arm*

8.1.2 *Assumptions of the Treatment Effect*

[REDACTED]

8.1.3 Sample Size and Power

According to [REDACTED]

[REDACTED]

[REDACTED]

[REDACTED]

Overall survival will be tested following the overall hierarchical testing procedure⁶⁴ upon demonstration of superiority in DFS at either interim or final analyses for all randomized subjects.

With the sample size [REDACTED]

[REDACTED]

8.1.4 Timing of the DFS and OS Interim and Final Analyses

Timing of the Interim and Final DFS Analyses

[REDACTED]

Timing of the Interim and Final OS Analyses

Based on the current design, the first interim OS analysis is planned at the time of the DFS interim analysis, and the second interim OS analysis is planned at the time of the DFS final analysis. [REDACTED]

[REDACTED]

final OS analyses will be derived based on the exact number of deaths observed

11. **What is the primary purpose of the *Journal of Clinical Endocrinology and Metabolism*?**

100% of the time, the system is available to the user.

[REDACTED]

8.1.5 *Potential Adjustment of Analysis Timing for DFS and OS*

As discussed in the [Section 8.1.1](#), there was no historical trial with the exact same population studied in this trial.

8.2 Populations for Analyses

- All Enrolled Subjects: All subjects who signed an informed consent form and were registered into the IWRS.
- All Randomized Subjects: All subjects who were randomized to any treatment arm in the study. This is the primary dataset for analyses of study conduct, study population, and efficacy.
- All Treated Subjects: All randomized subjects who received at least one dose of nivolumab or placebo during the study. This is the primary dataset for analyses of exposure and safety.
- PK Subjects: Subjects with available serum time-concentration data from randomized subjects dosed with nivolumab.
- Outcome Research subjects: randomized subjects who have an assessment at screening/baseline and at least 1 follow-up assessment
- Immunogenicity subjects: nivolumab treated subjects who have an assessment at screening/baseline and at least 1 follow-up assessment

- Biomarker subjects: All randomized subjects with available biomarker data (PD-L1 status and other assays).

8.3 Endpoints

8.3.1 Primary Endpoint

Disease-free survival is the primary endpoint of this study. Disease-free survival is the time between randomization date and first date of recurrence or death, whichever occurs first. Recurrence is defined as the appearance of one or more new lesions, which can be local, regional, or distant in location from the primary resected site (by imaging or pathology). DFS will be programmatically determined based on the disease recurrence date provided by the investigator. All deaths without prior recurrence will be included as DFS event - regardless of cause or of how long it has been since the last known disease evaluation. For subjects who remain alive and without recurrence, DFS will be censored on the date of last evaluable disease assessment.

Detailed censoring rules for the primary definition of DFS are presented in Table 8.3.1-1. (Sensitivity analyses of DFS will be described in the Statistical Analysis Plan [SAP]).

Table 8.3.1-1: Censoring Scheme Used in the Primary Definition of DFS

Situation	Date of Event or Censoring	Outcome
Recurrence ^{a,c}	Date of first recurrence	Event
Death ^{b,c} without recurrence	Date of death	Event
No baseline disease assessment	Date of randomization	Censored
No on-study disease assessments and no death	Date of randomization	Censored
No recurrence and no death	Date of last evaluable disease assessment	Censored
New anticancer therapy, tumor-directed radiotherapy, or tumor-directed surgery received without recurrence reported prior to or on the same day of disease assessment	Date of last evaluable disease assessment prior to or on the same date of initiation of subsequent therapy	Censored
Second non-esophageal and non-GEJ primary cancer reported prior to or on the same day of disease assessment	Date of last evaluable disease assessment prior to or on the same date of diagnosis of second non-esophageal and non-GEJ primary cancer	Censored

^a recurrence = appearance of one or more new lesions, which can be local, regional, or distant in location from the primary resected site

^b All deaths will be included as DFS event - regardless of cause or of how long it has been since the last known disease evaluation.

^c Without receiving preceding new anticancer therapy, tumor-directed radiotherapy, or tumor-directed surgery

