- After completion of the first two follow -up visits (FU 1 at day 30 days \pm 1 week and FU 2 at 84 days \pm 1 week from FU1),

See the details in [Table 5.1-3](#)

- Subjects who discontinue treatment for reasons other than distant recurrence will continue to have surveillance assessments (until distant recurrence) every 12 weeks \pm 1 week during the first year after randomization, every 12 weeks \pm 2 week during the second year, after that follow local standard in the range of 6-12 months between year 3 and year 5 with the last assessment at year 5. See the details in [Table 5.1-3](#)
- All adverse events will be documented for a minimum of 100 days after the last dose of study drug Subjects will be followed for drug-related toxicities until these toxicities resolve, return to baseline or are deemed irreversible. See the details in [Table 5.1-3](#)
- The Outcomes Research Assessments, Health Care Resource Utilization data collection, and biomarker sampling will continue as detailed in [Table 5.1-3](#)

[REDACTED]

[REDACTED]

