Procedure	Follow-up, Visits 1 and 2 ^a FU1: 30 days (\pm 7 days) FU 2: 84 days (\pm 7 days)	Survival Follow-Up Visits ^b [REDACTED] from FU2 (\pm 14 days)	Notes
Safety Assessments			
Targeted Physical Examination	X		
Adverse Events Assessment	X		Assessed using NCI CTCAE v. 4.0. See Sections 6.1.1 and 6.2.1 .
Review of Subsequent Cancer Therapy	X	X	
Review of Concomitant Medications	X		
Laboratory Tests	X		Include CBC w/differential, LFT's, BUN or serum urea level, creatinine, Na, K, Cl, LDH, Glucose, amylase, lipase, TSH (with reflexive Free T4 and Free T3. Total T3/T4 are acceptable if free T3/T4 are not available.) Urinalysis as clinically indicated To be done at FU1. To be repeated at FU2 if study related toxicity persists.
Pregnancy Test (WOCBP only)	X		Serum or urine pregnancy testing is only required at FU1 and FU2, unless increased frequency and duration is required per local regulations.
Efficacy Assessments			
Tumor Imaging Assessment	Every 12 weeks (\pm 7 days) \leq 12 months Every 12 weeks (\pm 14 days) $>$ 12 months through 24 months After that follow local standard in the range 6-12 months between year 3 and year 5 with the last assessment at year 5. Until distant recurrence. All time points are relative to the first dose of study treatment		See Section 5.4 .

Table 5.1-3: Follow-Up Procedural Outline (CA209-577)

Procedure	Follow-up, Visits 1 and 2 ^a FU1: 30 days (\pm 7 days) FU 2: 84 days (\pm 7 days)	Survival Follow-Up Visits ^b [REDACTED] from FU2 (\pm 14 days)	Notes
Outcomes Research Assessments			
EQ-5D	X	X	Prior to any assessments at FU1 and 2. [REDACTED] (\pm 14 days) after FU2, [REDACTED] [REDACTED] up to 2 years from last dose
FACT-E	X		Prior to any assessments at FU1 and 2.
ECS		X	[REDACTED] (\pm 14 days) after FU2, [REDACTED]
FACT-G7		X	[REDACTED] up to 2 years from last dose.
Health Care Resource Utilization	X		
Exploratory Biomarker Assessments			
[REDACTED]			
Subject Status			
Survival Status	X	X	[REDACTED] (\pm 14 days) or more frequently as needed after FU2, [REDACTED] [REDACTED] to include subsequent anticancer therapy.
Progression-free survival after the next line of subsequent therapy (PFS2)	X	X	Following first progression, subjects will continue to be followed during the safety and survival follow-up visits. Timing of second progression per investigator's assessments will be documented.

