- Begins after 1 year of treatment or when the decision is made to discontinue a subject from study therapy.
- After completion of the first two follow -up visits (FU 1 at day 30 days \pm 1 week and FU 2 at 84 days \pm 1 week from FU1), subjects will be followed every 3 months or more frequently as needed for survival.
- Subjects who discontinue treatment for reasons other than distant recurrence will continue to have surveillance assessments (until distant recurrence) every 12 weeks \pm 1 week during the first year after randomization, every 12 weeks \pm 2 week during the second year, after that follow local standard in the range of 6-12 months between year 3 and year 5 with the last assessment at year 5.

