4 ENDPOINTS

4.1 Efficacy Endpoints

4.1.1 Disease Free Survival

DFS is the primary endpoint.

Disease-Free Survival is time between randomization date and first date of recurrence or death, whichever occurs first. Recurrence is defined as the appearance of one or more new lesions, which can be local, regional, or distant in location from the primary resected site (by imaging or pathology). DFS will be programmatically determined based on the disease recurrence date provided by the investigator. For subjects who remain alive and without recurrence, DFS will be censored on the date of last evaluable disease assessment. The on-study disease assessment considers CT scan, MRI and biopsy

Detailed censoring rules for the primary definition of DFS are presented in Table 4.1.1-1; graphical display is presented in [Figure 2](#).

Table 4.1.1-1: Censoring Scheme Used in the Primary Definition of DFS

[figure not shown]
Situation	Date of Event or Censoring	Outcome
Recurrence (a) (c) (d) (e)	Date of first recurrence	Event
Death (b) (c) (d) without recurrence	Date of death	Event
No baseline disease assessment	Date of randomization	Censored
No on-study disease assessments and no death (d)	Date of randomization	Censored
Death with prior subsequent therapies or second non-esophageal and non-GEJ primary cancer (d)	Date of randomization	Censored
No recurrence and no death (d) (e)	Date of last evaluable disease assessment	Censored
New anticancer therapy, tumor-directed radiotherapy, or tumor-directed surgery received or the second non-esophageal and non-GEJ primary cancer date without recurrence or death reported prior to or on the same day of disease assessment (d) (e)	Date of last evaluable disease assessment prior to or on the same date of initiation of subsequent therapy or the second non-esophageal and non-GEJ primary cancer date whichever is earlier	Censored

Table 4.1.1-1: Censoring Scheme Used in the Primary Definition of DFS

(a) recurrence = appearance of one or more new lesions, which can be local, regional, or distant in location from the primary resected site
(b) All deaths will be included as DFS event - regardless of cause or of how long it has been since the last known disease evaluation.
(c) Without receiving preceding new anticancer therapy, tumor-directed radiotherapy, tumor-directed surgery, or second non-esophageal and non-GEJ primary cancer.
(d) Without baseline disease.
(e) With on-study disease assessment.

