7.5.3.5 Survival Rate Analysis

Survival rate analysis will be carried out only for those time points which are mature enough by the time of the given database-lock - i.e. minimum follow-up must be approximately longer than timepoint to generate the rate.

Survival rates at 6, 12, 18, 24, 36, 48 months and at 5 years will be provided using KM product-limit method. (Note that survival rates at 1, 2, and 3 years are positioned as secondary endpoints.) For each survival rate per treatment arm, two-sided 95% CIs using will be computed using the Greenwood's formula for variance derivation and on log-log transformation applied on the survivor function $S(t)$.

Note that although not positioned as secondary endpoint, DFS rates will also be provided at the same timepoints as survival rates.

[REDACTED]

whereby the confidence interval will be adjusted accordingly (i.e. using the recalculated nominal α level at the final OS analysis).

If the trial is stopped for superiority of DFS and OS at the second interim, the p-value from the second interim stratified log-rank test will be considered the final primary analysis result.

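### Recurrence scans end at year 5 but later deaths still count, so a descriptive DFS curve from a late lock is biased downward beyond about 60 months

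*Protocol*

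**What the plan says.** - **Imaging.** After the second year, scans follow local practice at intervals of "6-12 months between year 3 and year 5 with the last assessment at year 5" (Protocol 3.1; the same in Protocol Table 5.1-3 and SAP 2.1). None is scheduled after that.
- **Survival contact.** After the second follow-up visit, "subjects will be followed every 3 months or more frequently as needed for survival" (SAP 2.1), so deaths after year 5 are captured.
- **Deaths.** A death without prior recurrence is an event on its own date, "regardless of cause or of how long it has been since the last known disease evaluation" (Protocol 8.3.1; SAP Table 4.1.1-1, note b). The one limit is note c: "Without receiving preceding new anticancer therapy, tumor-directed radiotherapy, or tumor-directed surgery". The SAP adds second primary cancer to that note.
- **Survivors.** "For subjects who remain alive and without recurrence, DFS will be censored on the date of last evaluable disease assessment" (Protocol 8.3.1). SAP 4.1.1 defines what qualifies: "The on-study disease assessment considers CT scan, MRI and biopsy". A survival contact is not on that list.
- **Reporting.** SAP 7.5.2 asks for a DFS Kaplan-Meier plot and sets no upper time limit. SAP 7.5.3.5 lists survival rates up to 5 years, each given only if minimum follow-up roughly exceeds the timepoint, and adds that "DFS rates will also be provided at the same timepoints as survival rates".
- **Timing.** After first randomization, the DFS interim is projected at 48 months, the DFS final at 58 and the OS final at 77 (SAP Table 5.1-3). Revised Protocol 04 reports that deaths are accruing much more slowly than projected and adds a time-driven OS analysis.

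No visible text truncates DFS at the end of scheduled imaging.

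**The concern.** Once the year-5 scan has passed, whether a subject remains at risk for DFS depends on the later outcome. Someone alive and disease-free in year 7 is censored back at about month 60. Someone who dies without recurrence in year 7 stays at risk until death and counts as an event. The risk set beyond month 60 then consists almost wholly of people known to have failed, and Kaplan-Meier reads this as a hazard near 100%.

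SAP 5.1 expects a long plateau, and Table 5.1-1 puts the hazard after year 5 at only 0.003 (placebo) or 0.002 (nivolumab, as printed) per month. The long-term tail matters to readers of an adjuvant trial. Drawn by these rules from a late lock, it would show both arms collapsing and would hide the plateau.

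**Working it through.** **1. Reproduce the plan's DFS curve** (SAP Table 5.1-1: control hazards with piecewise hazard ratios).

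- Placebo at 60 months: exp[−(0.035×12 + 0.03×18 + 0.02×30)] = exp(−1.56) = 21.0%.
- Nivolumab at 60 months: exp[−(0.105 + 0.667×(0.315 + 0.54 + 0.60))] = exp(−1.0755) = 34.1%.
- At 120 months: 21.0% × exp(−0.003×60) = 17.5%. With hazard 0.003×0.8 = 0.0024, 34.1% × exp(−0.0024×60) = 29.5%.

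All four match the table. The true 72-month values follow: 21.0% × exp(−0.036) = 20.3% and 34.1% × exp(−0.0288) = 33.1%.

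**2. Choose a lock date.** Accrual is 36 months (SAP 5.3). The SAP's own 5-year rate becomes mature at about 36 + 60 = 96 months, so 96 is used as an illustration; the documents do not name it. The projected 77-month lock is taken as well.

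**3. Expected DFS events after month 60.** Assume uniform accrual, 507 and 253 subjects, and that every DFS event after month 60 is a death. Follow-up beyond month 60 is then uniform on 0 to w, with w = 36 (lock 96) or 17 (lock 77). Expected events = N × S(60) × (w/36) × [1 − (1 − e^(−hw))/(hw)].

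| Lock | Arm | Disease-free at month 60, followed beyond it | Expected later deaths | Still alive, censored by month 60 |
|---|---|---|---|---|
| 96 | Nivolumab | 507×0.341 = 172.9 | 172.9×0.0420 = 7.3 | 165.6 |
| 96 | Placebo | 253×0.210 = 53.1 | 53.1×0.0521 = 2.8 | 50.4 |
| 77 | Nivolumab | 172.9×17/36 = 81.6 | 81.6×0.0201 = 1.6 | 80.0 |
| 77 | Placebo | 53.1×17/36 = 25.1 | 25.1×0.0251 = 0.6 | 24.5 |

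**4. What Kaplan-Meier does with them.** If k subjects remain and all will die, the product is (1 − 1/k)(1 − 1/(k−1))…(1 − 1/1) = 0. The chance of at least one such death is about 1 − e^(−expected deaths): 99.9% and 94% at lock 96, and 81% and 47% at lock 77 (nivolumab, placebo). With no such death the curve simply stops near month 60.

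Before the last death, the curve equals S(60) times the share of the k deaths still to come. At lock 96 that share is about (1 − s/36)², where s is months past 60. At 72 months it is (2/3)² = 0.444, giving 15.2% (nivolumab) and 9.3% (placebo). At 84 months it is (1/3)² = 0.111, giving 3.8% and 2.3%.

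**5. Simulation** (150 runs per scenario; Table 5.1-1 hazards; scans every 12 weeks to month 24, then an assumed mix of 6- and 12-monthly scans to month 60; lock 96 months).

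| 72-month DFS | Nivolumab | Placebo |
|---|---|---|
| True | 33.1% | 20.3% |
| Plan's rule | 15.0% | 8.2% |
| Plan's rule, ±2-month scan window after month 24 | 16.7% | 10.5% |
| Plan's rule, 10% of subjects scanned yearly after year 5 | 26.0% | 15.0% |
| Control: event-free subjects censored at cut-off | 33.0% | 20.2% |

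Under the plan's rule the 84-month values are 3.7% and 1.8%. The curve ends at zero in 100% and 96% of runs at lock 96, and in 81% and 39% at lock 77. The control row isolates the censoring rule as the cause. It is not the remedy, because it treats unscanned survivors as known to be recurrence-free.

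**6. The 60-month rate.** The plan's rule gives 34.0% and 21.0% against true values of 34.1% and 21.0%. With the ±2-month window it gives 33.7% and 20.7%. A separate simulation dating recurrence at the next scan gives 35.1% and 21.9%. All are within about 1 point.

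**The case against.** The strongest reply is about reach, and most of it stands.

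- **No DFS rate beyond 5 years is planned.** The SAP 7.5.3.5 list ends there, behind a maturity condition. At the projected OS final analysis the last subject has 41 months of follow-up, so on that condition rates stop at 36 months. The 66- or 72-month values describe the plotted curve, not a scheduled estimate.
- **DFS testing is over by then.** SAP Table 5.1-3 shows DFS as not applicable at the OS final analysis. A DFS curve at that lock is inferred from 7.5.2, which sets no time limit on the plot, and 7.5.3.5, which ties DFS rates to survival rates at the given lock. It is not an explicit instruction.
- **The size is fragile.** It rests on a handful of deaths. At 77 months the placebo arm often has none after month 60. SAP 4.1.1 does not restrict assessments to scheduled ones, so off-schedule scans soften the fall. Deaths after new therapy do not count.
- **Absence is not proven.** Parts of Protocol 8.1.4, 8.4.2.2 and 8.5.1 are redacted or blank. The visible SAP (version 4.0, September 2020) predates Revised Protocol 04 (April 2024).

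What survives is the mechanism. The nearest planned check, for two or more consecutive missing assessments, runs only if at least 10% of DFS events are affected. It does not clearly apply when no assessment is due.

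**Conclusion.** The point holds as a minor one about descriptive reporting. Under the visible rules, a DFS curve from any lock more than 60 months after first randomization is biased downward beyond about month 60. At a 96-month lock it almost always ends at zero, with a 72-month error of roughly 12 points (placebo) and 18 points (nivolumab) if no one is scanned after year 5. If 10% have yearly scans, the error is about 5 and 7 points. At 77 months the drop to zero is likely for nivolumab and less than even for placebo. These sizes assume the SAP's hazards, uniform accrual, the scan pattern above and no recurrences found after year 5; the direction does not depend on them.

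A reader might infer that the primary DFS comparison or the 5-year DFS rate is compromised. The documents do not support that. At 48 and 58 months after first randomization nobody has 60 months of follow-up, and the 60-month estimate moves by about 1 point at most. Nor do they support reading the late collapse as certain to be published, since no DFS output beyond 5 years is listed.

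**What to change.** Leave the primary DFS definition in Protocol 8.3.1 and SAP 4.1.1, and the DFS interim and final tests, as they are. A censoring rule in the primary definition that depended on the cut-off date would be worse than the problem. Add to SAP 7.5.2 and 7.5.3.5:

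*In descriptive DFS updates after the DFS final analysis, DFS follow-up is truncated at month 60 for all subjects. Deaths after month 60 count in OS only. Event-free subjects, including those who missed the year-5 scan, are censored at their last assessment on or before the end of the year-5 scan window. DFS Kaplan-Meier curves and rates are not shown beyond 60 months.*

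The imaging schedule gives day windows only through month 24, so the SAP must also define the year-5 window for this purpose.

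The cost is a short SAP addition and the loss of a few late deaths from descriptive DFS: about 3 placebo and 7 nivolumab at a 96-month lock, and about 1 and 2 at 77 months. All remain in OS. A small residue stays, because a death between the last scan and month 60 still counts while a survivor is censored at that scan; at 60 months this is worth under 1 point.

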- h) Any serious or uncontrolled medical disorder or active infection that, in the opinion of the investigator, may increase the risk associated with study participation, study drug administration, or would impair the ability of the subject to receive protocol therapy.
- i) Known history of positive test for human immunodeficiency virus (HIV) or known acquired immunodeficiency syndrome (AIDS). NOTE: Testing for HIV must be performed at sites where mandated by local regulation
- j) Prior malignancy active within the previous 3 years except for locally curable cancers that have been apparently cured, such as basal or squamous cell skin cancer, superficial bladder cancer, or carcinoma in situ of the prostate, cervix, or breast.
- k) Subjects who have received a live/attenuated vaccine within 30 days of the first treatment.

3.3.2.3 *Physical and Laboratory Test Findings*

- a) Any positive test result for hepatitis B virus or hepatitis C virus indicating presence of virus, e.g. Hepatitis B surface antigen (HBsAg, Australia antigen) positive, or Hepatitis C antibody (anti-HCV) positive (except if HCV-RNA negative)..

3.3.2.4 *Allergies and Adverse Drug Reaction*

- a) History of allergy or hypersensitivity to study drug components.
- b) History of severe hypersensitivity reaction to any monoclonal antibody.

3.3.2.5 *Other Exclusion Criteria*

- a) Prisoners or subjects who are involuntarily incarcerated
- b) Subjects who are compulsorily detained for treatment of either a psychiatric or physical (eg, infectious disease) illness

Eligibility criteria for this study have been carefully considered to ensure the safety of the study subjects and that the results of the study can be used. It is imperative that subjects fully meet all eligibility criteria.

3.3.3 *Women of Childbearing Potential*

Women of childbearing potential (WOCBP) is defined as any female who has experienced menarche and who has not undergone surgical sterilization (hysterectomy, bilateral salpingectomy, or bilateral oophorectomy) and is not postmenopausal. A postmenopause state is defined as 12 months of amenorrhea in a woman over age 45 years in the absence of other biological or physiological causes. In addition, females under the age of 55 years must have a serum follicle stimulating hormone, (FSH) level > 40 mIU/mL to confirm menopause.

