7.5.2 Primary Efficacy Endpoint

DFS will be compared between treatment arms using a two-sided log rank test, stratified by the three randomization stratification factors as recorded in IWRS.

The HR for DFS with its corresponding two-sided $100 \times (1 - \text{adjusted } \alpha)\%$ CI will be estimated via a stratified Cox model with treatment arm as the only covariate in the model. Adjustment on the CI will be based on the reallocated alpha level.

DFS for each treatment arm will be estimated and plotted using the KM product-limit method. Median survival time will be computed using the KM estimate and a 95% CI for the median will be computed based on a log-log transformation of the survivor function.

Source of DFS Event

The source of DFS event will be summarized by treatment group:

- Recurrence (local recurrence, regional recurrence, distant recurrence)
- Death

Status of Censored Subjects

The status of subjects who are censored in the DFS KM analysis will be tabulated for each randomized treatment group using the following categories:

- 1) Censored on randomization date
 - a) no baseline disease assessment
 - b) no on-study disease assessment and no death
 - c) no on-study disease assessment but death with prior subsequent therapy or second primary cancer
- 2) Censored on date of last evaluable disease assessment on-study
 - a) Received subsequent anti-cancer therapy
 - b) Second non-esophageal and non-GEJ primary cancer
 - c) Still on treatment
 - d) In follow-up
 - e) Off study
 - i) lost to follow-up
 - ii) subject withdrew consent
 - iii) other

DFS rates at fixed time points (e.g. 6 months, depending on the minimum follow-up) will be presented along with their associated 95% CIs. These estimates will be derived from the Kaplan-Meier estimate and corresponding CIs will be derived based on Greenwood formula for variance derivation and on log-log transformation applied on the survivor function.

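### Under the SAP, any second non-esophageal, non-GEJ primary, however trivial, ends primary DFS follow-up and later recurrences or deaths are not counted; the protocol contradicts itself on the same point

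*Protocol*

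**What the plan says.** **Protocol, Section 8.3.1.** The last row of Table 8.3.1-1 is triggered by "Second non-esophageal and non-GEJ primary cancer reported prior to or on the same day of disease assessment". It censors DFS at the last evaluable assessment on or before that diagnosis. Footnote c, attached to the two event rows, makes a recurrence or death an event if it occurs "Without receiving preceding new anticancer therapy, tumor-directed radiotherapy, or tumor-directed surgery"; second primaries are not in that list. Footnote b reads "All deaths will be included as DFS event - regardless of cause", and the section text counts every death without prior recurrence.

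**SAP, Section 4.1.1.** Table 4.1.1-1 has two rows that mention second primaries. One censors at the last evaluable assessment on or before the second primary or the start of subsequent therapy, whichever is earlier. The other, "Death with prior subsequent therapies or second non-esophageal and non-GEJ primary cancer (d"), censors at the date of randomization. Footnote (c) is wider than the protocol's: "Without receiving preceding new anticancer therapy, tumor-directed radiotherapy, tumor-directed surgery, or second non-esophageal and non-GEJ primary cancer". Footnote (b) still says that all deaths are events.

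**SAP, Section 7.5.2.** Among subjects censored at randomization, the matching category is "no on-study disease assessment but death with prior subsequent therapy or second primary cancer".

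**Eligibility.** Exclusion criterion j (Protocol Section 3.3.2.2) bars subjects who had another active cancer in the last 3 years. Its exception reads "except for locally curable cancers that have been apparently cured, such as basal or squamous cell skin cancer". It also names superficial bladder cancer and in situ cancer of the prostate, cervix or breast.

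Neither document defines a second primary for censoring or exempts any type of cancer.

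**The concern.** DFS is meant to capture recurrence of the resected cancer, or death. A skin cancer removed in clinic says nothing about either. Under the SAP's wording it still ends the subject's contribution to the primary analysis, and an esophageal recurrence found at a later scheduled scan is not counted. Surveillance continues until distant recurrence (Protocol Sections 3.1 and 3.6), so the trial would normally still collect that event.

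What is at stake is a small number of genuine primary-endpoint events, the timing of the 374- and 440-event triggers, and the lack of one consistent rule. Two programmers, one working from each document, could derive different DFS outcomes for the same subject.

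**Working it through.** **1. The rule, document against document.** Take a subject with on-study scans who has a basal cell carcinoma excised and later has an esophageal recurrence or dies.

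| Source | Later recurrence | Later death |
|---|---|---|
| Protocol table, last row | censored | censored |
| Protocol footnotes b, c and text | event | event |
| SAP footnote (c) | not an event | not an event |
| SAP footnote (b) | – | event |
| SAP row on death after a second primary | – | censored at randomization |
| SAP row on subsequent therapy or second primary | censored at last scan on or before it | – |

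Only the SAP removes the later events explicitly. Its row on death after a second primary carries note (d), no disease at baseline, but not note (e), an on-study assessment. As written, it therefore also sends subjects with scans back to the date of randomization. Section 7.5.2 confines that category to subjects with no on-study assessment.

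**2. Is the censoring needed for attribution?** Protocol Section 5.4.1 already says that a lesion found to be a malignancy of non-esophageal, non-GEJ origin does not indicate recurrence. A second primary is kept out of the event count without censoring the subject.

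**3. Does a planned analysis restore the events?** The no-truncation analysis in SAP Section 7.5.2.1 lifts censoring for subsequent anti-cancer therapy. None of the listed sensitivity analyses names second primaries.

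**4. The plan's own power.** Inputs from SAP Sections 5.3 and 5.4: 440 events, average HR 0.72, 2:1 allocation, two-sided 0.05. Schoenfeld power is Φ(√(d × 2/9) × |ln HR| − 1.96) = Φ(√97.8 × 0.3285 − 1.96) = Φ(1.288) = 90.1%. With Lan-DeMets O'Brien-Fleming spending at 374 and 440 events, the nominal levels are 0.0301 and 0.0414 (stated 0.03 and 0.042) and cumulative power is 79.6% and 89.5% (stated 81% and 91%). The stated figures reproduce to within 2 points.

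**5. Size under assumed rates.** The inputs are the SAP Table 5.1-1 hazards, 760 subjects, uniform accrual over 36 months, a 58-month cut, no other dropout, and second primaries independent of DFS at a constant rate λ. Per arm, expected events without the rule are ∫h(t)S(t)G(t)dt, where G(t) is the probability of follow-up beyond t. With the rule, the integrand is multiplied by exp(−λt). Without the rule, 447 events are expected.

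| Assumed rate per 100 person-years | Subjects censored | Events lost | Share of 447 | Power at the same calendar time |
|---|---|---|---|---|
| 0.5 | 7.7 | 2.7 | 0.6% | 89.9% |
| 1 | 15.3 | 5.5 | 1.2% | 89.8% |
| 2 | 30.1 | 10.8 | 2.4% | 89.4% |

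Power uses 440 × (events kept ÷ 447). At 2 per 100 person-years this is 440 × 436.2/447 = 429.4 events and Φ(1.249) = 89.4%, a fall of 0.7 points from 90.1%.

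A separate simulation, cut at 440 events instead of at month 58, agrees: 7.5, 14.8 and 29.3 subjects censored, and 2.7, 5.2 and 10.4 events lost.

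**6. Timing.** The same simulation moves the 440-event cut by 0.5, 1.0 and 2.1 months. As a rough check, the SAP projects 374 events at month 48 and 440 at month 58, or 66/10 = 6.6 per month. Dividing 2.7, 5.5 and 10.8 by 6.6 gives 0.4, 0.8 and 1.6 months. The simulated delays are slightly longer because events arrive more slowly towards the end.

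**The case against.** **Criterion j governs entry, not follow-up.** This stands. It concerns cancer history at entry, requires apparent cure, and does not say that such cancers are irrelevant on study. A reader might infer that the censoring rule contradicts eligibility; it does not. The criterion is useful only as a ready list of cancers the sponsor already treats differently.

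**The protocol does not clearly discard anything.** This also stands. A reader might infer from the shared row that both documents drop later events. Protocol footnotes b and c and the section text point the other way, so the loss rests on the SAP.

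**The numbers are assumptions, and may be high.** This stands in part. A constant detection rate over all of DFS follow-up is generous: routine AE collection ends about 100 days after the last dose (Protocol Sections 6.1.1 and 6.2.1), and Table 5.1-3 has no AE assessment at survival visits. How a later skin excision would be captured is not stated. Lost events are also replaced, because the analysis is event-driven.

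**Unequal censoring by arm.** A reader might infer that skin reactions on nivolumab lead to more skin examination and so more censoring in that arm. Nothing in the documents links the two, and the trial is double-blind. That inference is not supported.

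**It is late to change.** The rationale for Revised Protocol 04 says the first planned interim analysis is complete, and SAP Section 5.4 places the DFS interim at that look. This limits how the change can be applied, not whether the rule should be clarified.

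**Conclusion.** The concern holds as a matter of scope and consistency. Under the SAP, any second non-esophageal, non-GEJ primary, including a trivial one, ends primary DFS follow-up, and no listed sensitivity analysis clearly undoes this. That a basal cell or in situ cancer triggers the rule follows from the literal wording and the absence of an exemption; neither table names these cancers. The protocol disagrees with itself, and the SAP's rows and footnotes disagree with one another on deaths.

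The likely effect is small: about 3 to 10 of 440 events, less than 1 point of power at a fixed calendar time, and about 0.5 to 2 months on the 440-event cut. This rests on assumed rates of 0.5 to 2 per 100 person-years, a constant rate, and independence from DFS; the documents supply no rate. Recurrences before the second primary still count, and OS is unaffected. The material does not support a claim that the primary result is biased or the trial underpowered. The case for change is that it restores genuine endpoint events cheaply and removes a contradiction from the primary endpoint.

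**What to change.** 1. In Protocol Table 8.3.1-1 and in SAP Table 4.1.1-1 (both second-primary rows and footnote (c)), limit the trigger to second primaries outside a closed list of locally curable or in situ cancers, using those named in exclusion criterion j. The list must be closed, because criterion j's own wording is open-ended.
2. State that local treatment of a listed lesion does not count as new anticancer therapy, tumor-directed radiotherapy or tumor-directed surgery for DFS censoring. Otherwise the subject is censored through the subsequent-therapy row instead.
3. Align Protocol footnote c with SAP footnotes (b) and (c), so that both documents say the same about recurrences and deaths after a second primary.
4. Reconcile the SAP row that censors death after a second primary at randomization with Section 7.5.2, which limits that category to subjects with no on-study assessment.
5. Classify recorded second-primary terms blinded, before database lock. For any DFS analysis already locked, report the narrower definition as a labelled supplementary analysis and leave the locked result as it is.

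The cost is a footnote and aligned wording in each table, plus blinded coding of the cancer type for the recorded second primaries, about 8 to 30 subjects under the assumed rates.
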